7.5.1.3 Dose and Application

The dose and duration of stimulation administered under the active and sham conditions will remain identical for all participants. Under the active condition, 2mA of current will be delivered for 30 minutes. Under the sham condition, only brief pulses will be administered during the 30-minute session.

1. On each study day just prior to the application of electrodes, a participant's head will be measured in order to identify their F3 location.
2. The sponge electrodes will be moistened with saline prior to insertion of the rubber electrode and placement on a participant's head.
3. Electrodes will be affixed via adjustable rubberized straps.
4. The numerical condition code will be entered into the NeuroConn DC Stimulator Plus device, which will then administer 30 minutes of either active or sham stimulation.

7.5.2 NeuroConn DC Stimulator Plus

tDCS has been established as a valid and reliable tool for at least temporarily affecting brain and behavior with minimal risks (for review, see ²² and ⁴³). Stimulation will be delivered by a NeuroConn DC Stimulator Plus (Model 0021), which is a battery-driven constant current stimulator. See Figure 4. The NeuroConn stimulator is certified as an active medical device (class IIa) by the European Union Notified Body 0118, and has been safely used in scores of published tDCS studies around the world.

Figure 4.

The stimulator is not connected to a mainline power source and cannot produce more than 4.5 mA of current. The current density, as indexed by stimulation strength (A)/electrode size, is a relevant parameter for inducing neuronal damage ⁴⁴. We will be remaining within the recommended current density safety guidelines of $40 \mu\text{C}/\text{cm}^2 * \text{ph}$ ⁴⁴. We also reviewed the safety notes in the operator manuals provided by the manufacturer of the device. The stimulation parameters in the planned investigation do not exceed the stimulation limits or violate the safety directives specified in the operator manual.

The active constant current and sham current settings both enable an impedance control that reliably detects any electrode disconnection. In the event of an electrode disconnection, the experimenter is alerted and the device automatically stops delivering current. The 30-minute dose delivery session is paused briefly while the electrode is quickly reaffixed to the head, reinitiating the electrical circuit. The 30-minute stimulation session is promptly resumed.

We will use non-metallic, conductive rubber electrodes covered by saline-soaked sponges to minimize the potential for chemical reactions at the interface of the scalp or skin and the electrodes.

Following IRB approval, the NeuroConn DC Stimulator Plus device will undergo evaluation by Johns Hopkins Clinical Engineering. Both active and sham tDCS will be administered by a trained study team member.

7.5.3 Cognitive tasks during stimulation

During each stimulation session under both active and sham tDCS conditions, participants will engage in a computerized working memory n-back task that continuously adapts to the performance of the individual, remaining equally engaging and demanding over the course of training and across individuals of varying working memory ability ^{45,46}.

7.6 Study Assessments

Participants are expected to spend no longer than two hours completing cognitive testing and questionnaires on any given study day. This battery of cognitive tools and questionnaires consists of instruments that are routinely used in the clinical setting with medically frail and elderly patients. Their completion is not expected to result in increased fatigue in study participants. Nonetheless, breaks will be taken as necessary and appropriate in order to facilitate participant comfort and engagement.

7.6.1 Screening Instruments

Screening instruments will be administered at study entry and will take approximately 12 minutes to complete.

- 7.6.1.1 Mini Mental State Exam (MMSE;⁴⁷). Participants will complete the MMSE, a brief cognitive screening measure that assesses orientation, attention, learning/memory, language functioning, and visuoconstruction skills. Administration requires approximately five minutes and will be used to ensure that all participants meet our stated inclusion criteria (i.e., non-demented as defined by a MMSE score ≥ 24).
- 7.6.1.2 CAGE⁵¹. The CAGE questionnaire is a widely used 4-item screening instrument for problem drinking. Each item is scored 0 (absent) or 1 (present). Scores ≥ 2 are considered clinically significant. Scores on the CAGE along with the patient's report of the number of alcoholic drinks consumed per week will be used to ensure that all participants meet our stated inclusion criteria with respect to alcohol consumption. Included within Appendix P.
- 7.6.1.3 Quantitative Fatigue Assessment. Potential participants will be asked to rate their fatigue on a 0 (no fatigue) to 10 (worst fatigue imaginable) scale in order to ensure that the study enrollment is limited to those with reports of at least moderate fatigue, as stated in our inclusion criteria. Consistent with ASCO guidelines for assessment of fatigue in cancer⁵², scores of ≥ 4 will be considered indicative of at least moderate fatigue.

7.6.2 Tools to Assess Primary and Secondary Endpoints

The primary and secondary endpoints will be assessed at the beginning and end of each five-day study wave in-person (i.e., subjective cognition and fatigue), and approximately seven days after the last stimulation session by phone (i.e., subjective cognition and fatigue). In-person testing will take approximately 20 minutes; whereas, testing via phone will take approximately 10 minutes.

- 7.6.2.1 Paced Auditory Serial Attention Test (PASAT)^{1,2}. The primary measurement tool for assessing objective cognitive functioning will be performance on the PASAT.

The PASAT is working memory task that has been well-validated medical populations including breast cancer⁵³. Test administration involves the aural presentation of single digits via computer in order to ensure a standardized rate of stimulus presentation. Stimuli are presented every three seconds (trial 1) or every two seconds (trial 2). Participants add each new digit to the one immediately prior as the test continues to

present stimuli. The test score reflects the total number of correct sums given (out of 60 possible) in each trial.

Two equivalent, alternative PASAT forms will be used to minimize practice effects. The test takes approximately 10 minutes to complete. It will be completed prior to and following both five-day active anodal and sham stimulation conditions (i.e. on four occasions). Available data indicates that prior to adjuvant treatment, breast cancer patients with stage I-III disease score an average of 46.6 ± 11.2 on the PASAT trial 1 (3 second administration) and an average of 34.3 ± 10.1 on trial 2 (2 second administration)⁵⁴.

7.6.2.2 Functional Assessment of Cancer Therapy Cognitive Scale (FACT-Cog version 3)⁵⁵. The measurement endpoint for subjective cognition will be scores on the FACT-Cog, a 37-item self-report measure addressing cognitive difficulties and their effect on patient quality of life. The measure addresses six cognitive domains (memory, concentration, mental acuity, verbal fluency, functional interference, and multitasking). The questionnaire is easy to use and appropriate for individuals with a history of cancer of varying age groups and backgrounds.

Responses are provided on 5-point Likert scales addressing the frequency with which each type of cognitive difficulty occurred from 0, “never” to 4, “several times a day” over the prior seven days. Two additional subscales address “noticeability” or comments from others regarding cognition and “effect of perceived cognitive impairment on quality of life.” These are rated on 5-point Likert scales ranging from 0, “not at all” to 4, “very much.” The total FACT-Cog score is obtained by summing the individual subscale scores and ranges from 0 to 148. Breast cancer patients produce a mean FACT-Cog total score of 119.0 ± 23.3 .⁵⁶

The FACT-Cog takes approximately 5 minutes to complete. It will be completed prior to and following both five-day active anodal and sham stimulation conditions (i.e. on four occasions). It will also be completed by phone (taking approximately 5 minutes) seven days (\pm three days) after the final (fifth) stimulation session of each study wave in order to assess for persistence of stimulation effects.

7.6.2.3 Multidimensional Fatigue Symptom Inventory 30-item short form (MFSI-SF)⁵⁷. The primary measurement tool for subjective fatigue will be the MFSI-SF, which assesses participants’ subjective ratings across five empirically derived subscales (general fatigue, physical fatigue, emotional fatigue, mental fatigue, and vigor). Responses are provided on 5-point Likert scales addressing the extent to which each symptom was experienced during the preceding week (0, not at all to 4, extremely). The five subscale scores are obtained by summing scores within each subscale. The MFSI-SF total score is obtained by subtracting the vigor subscale score from the sum of the four fatigue subscales. Scores range from -36 to 144.

The MFSI-SF is well validated in breast cancer patients^{58,59}. Breast cancer patients with fatigue produce an average score of 14.7 ± 15.2 ⁶⁰.

The MSFI-SF takes approximately 5 minutes to complete. It will be completed by all study participants prior to and following both five-day active anodal and sham stimulation conditions (i.e. in person on four occasions). It will also be completed by phone (taking approximately 5 minutes) approximately seven days (\pm three days) after the final (fifth) stimulation session of each study wave in order to assess for persistence of stimulation effects.

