stimulation of the left DLPFC, as working memory performance remained unchanged in response to both cathodal stimulation of the left DLPFC and anodal stimulation of the left primary motor cortex. Similar improvements in working memory have been seen after tDCS in patients with stroke²⁹, Parkinson's disease³⁰, and major depression³¹. In a case study of a single breast cancer survivor, tDCS was found to be safe and tolerable while resulting in improvements in cognitive functioning for approximately two weeks³². In multiple sclerosis, tDCS applied to the DLPFC has also repeatedly been shown to be safe and tolerable resulting in reduced fatigue ratings, with effects lasting up to three weeks following active stimulation³³⁻³⁵.

Studies of tDCS provide evidence to suggest that sustained and repeated stimulation paradigms can prove effective in generating prolonged treatment effects. Depending upon the duration of stimulation, and the experimental situation, effects of tDCS have been found to persist for minutes, hours, or up to a month^{36,37}. For example, a single 13-minute session of motor cortex stimulation has yielded up to 90 minutes of altered cortical excitability²⁴, and consecutive daily sessions of tDCS were associated with a significant behavioral improvement lasting up to two weeks post-treatment in individuals experiencing post-stroke motor dysfunction³⁶. With respect to cognitive enhancement, it has been demonstrated that repeated daily anodal tDCS applied to the DLPFC results in improvements in working memory that last up to a week or longer in adults with major depression³⁸, and these cognitive enhancements are independent of tDCS-induced changes in mood functioning. In multiple sclerosis, repeated daily stimulation aimed at reducing neuropathic pain yielded significantly diminished pain ratings three weeks following the termination of stimulation and was not associated with any adverse reactions³⁷. Similarly, improvements in subjective fatigue ratings have been demonstrated to persist for up to three weeks following tDCS in multiple sclerosis³³ and two weeks in a participant with breast cancer³².

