7. STUDY DESIGN AND TREATMENT PLAN

7.1 Summary

We propose a straightforward randomized sham-controlled double-blind crossover trial of active tDCS versus sham tDCS.

Participants will complete two five-day study waves separated by a four-week washout period. During each wave, participants will complete a brief cognitive battery and study questionnaires on the first and last day of the study wave (i.e., Monday and Friday). On all five days of each wave, participants will engage in cognitive tasks while receiving stimulation (either active or sham) in order to maximize stimulation effects ²⁷. In order to assess for duration of subjective effects, participants will complete self-report measures of subjective fatigue, mood, and cognition by phone approximately seven days after the final day of the first study wave. After a washout period of four weeks, participants will repeat a second study wave wherein they engage in the same study procedures while receiving the opposite stimulation condition (active/sham); again followed by a phone call for subjective ratings of fatigue, mood, and cognition.

Basic Study Schedule*				
Days 1 – 5	Day 12	Days 6 – 35	Days 36 – 40	Day 47
Wave 1 5 consecutive daily study visits (Monday-Friday)	15-minute study phone call	Washout No study activities	Wave 2 5 consecutive daily study visits (Monday-Friday)	Follow-up 15-minute study phone call

* See Study Calendar, Section 8, for detailed schedule and scheduling windows/allowances.

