8. STUDY CALENDAR

Procedure	Screening	Intervention							End of Study
		Day(s)							
		1	2-4	5	12 ^b	36	37-39	40	47 ^b
Approximate Duration of Participation (minutes)	12	140	45	115	10	115	45	115	10
Consent, Demographics, Medical and Cancer History	X								
Concomitant Medication and Supplement Use	X					X			
Mini Mental State Exam	X								
CAGE	X								
Quantitative Fatigue Assessment	X								
Transcranial Direct Current Stimulation (active/sham)		X	X	X		X	X	X	
Computerized Working Memory Task ^a		X	X	X		X	X	X	
Paced Auditory Serial Attention Test		X		X		X			X
Functional Assessment of Cancer Therapy Cognitive Scale		X		X	X	X			X
Multi-dimensional Fatigue Symptom Inventory		X		X	X	X			X
Hopkins Verbal Learning Test-Revised		X		X		X			X
Brief Visuospatial Memory Test-Revised		X		X		X			X
Trail Making Test Parts A and B		X		X		X			X
Calibrated Ideational Fluency Assessment		X		X		X			X
WAIS-IV Digit Span Subtest		X		X		X			X
Grooved Pegboard Test		X		X		X			X
Hospital Anxiety and Depression Scale		X		X	X	X			X
Pittsburgh Sleep Quality Index		X		X		X			X
EORTC Quality of Life Questionnaire		X		X		X			X
History Form		X							
Hopkins Adult Reading Test		X							
Edinburgh Inventory		X							
UCLA Loneliness Scale		X							
NEO-Five Factor Inventory - 3		X							
Side Effect Questionnaire ^c		X	X	X		X	X	X	

- a. Computerized working memory task is administered during transcranial direct current stimulation
- b. Day 12 and Day 47 assessments will be performed by phone -1/+3 days of days 12 and 47.
- c. The side effect questionnaire will be completed before and after each transcranial direct current stimulation session (a total of 20 times). On days 5 and 40, participants will be asked if they believed they were receiving active or sham tDCS during the wave they have just completed and to rate their degree of confidence with respect to these judgments.

NOTE: If there is a greater than 21-day period between the screening procedures/determination of eligibility and the initiation of the study intervention, participants will be re-screened during an appointment reminder phone call approximately one week prior to the study intervention. We will permit a between-wave washout period of five rather than four weeks, in which case the second

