wave and end of study will be delayed by seven days. The schedule should be followed as closely as is realistically possible; however, the schedule may be modified due to problems such as scheduling delays or conflicts (e.g., clinic closure, poor weather conditions, vacations, etc.) with the guidance of the Principal Investigator/designee, as appropriate, and will not be reportable as a deviation unless the endpoints of the study are affected.

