12.3 Analysis Plan

The comparison between active tDCS and shame stimulation in change in PASAT score will be performed using a two-sided paired t-test based on data from participants who complete the crossover experiments. We will also use a linear mixed effects model to evaluate the effect of tDCS in the change in PASAT score by including data from all participants who complete at least one study wave.

For secondary and exploratory endpoints, pre- and post-stimulation scores, including scores on the PASAT, FACT-Cog, and MFSI-SF, and the corresponding changes in scores (post-pre) after five consecutive days of stimulation will be summarized using descriptive statistics and displayed graphically for each stimulation condition. Data may be transformed as appropriate to reduce skewness and improve symmetry. To account for correlation among multiple measurements within the same patient, linear mixed effects models will be used to evaluate the effect of tDCS, where the outcome is the change in scores (post-pre stimulation) and the covariates will include the indicator of the stimulation condition. Other covariates in the exploratory analyses may include but not be limited to the order of the experiments (for assessing carryover effects), number of days receiving active/sham stimulations, baseline fatigue, depression, anxiety, loneliness, handedness, cancer stage, and cancer treatment. The change in MFSI-SF and FACT-Cog score obtained (via phone) seven days after each study wave will be analyzed using the same approach. Exploratory sensitivity analyses will be carried out to examine if dropout/missingness is informative.

Data analyses will be performed by the study statistician, [name].

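### The two windows for the persistence phone call conflict at the early limit, and both let the seven-day recall of FACT-Cog and MFSI-SF reach into the stimulation week

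*Combined protocol and SAP*

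**What the plan says.** Objective 3.1.4 and hypothesis 4.2.3 ask whether effects on subjective cognition and fatigue last to about a week after the last stimulation. The data are FACT-Cog and MFSI-SF ratings taken by phone after each wave.

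The window for that call is given twice. Sections 7.6.2.2 and 7.6.2.3, in the same terms for both scales, set it at seven days (plus or minus "three days) after the final (fifth) stimulation session of each study wave in order to assess for persistence of stimulation effects". The calendar says: "Day 12 and Day 47 assessments will be performed by phone -1/+3 days of days 12 and 47". The schedule table in Section 7.1 points to the calendar: "See Study Calendar, Section 8, for detailed schedule and scheduling windows/allowances". No sentence states which section prevails.

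Section 8 also contains two allowances. On timing in general, "the schedule may be modified due to problems such as scheduling delays or conflicts", and such changes are not reportable unless they affect endpoints. On the gap between waves, "We will permit a between-wave washout period of five rather than four weeks", which moves the second wave and its call by seven days.

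Section 7.6.2 describes FACT-Cog as covering the previous seven days and MFSI-SF as covering the previous week.

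Section 12.3 handles the phone scores in one sentence: "The change in MFSI-SF and FACT-Cog score obtained (via phone) seven days after each study wave will be analyzed using the same approach". Its covariate list is open-ended ("Other covariates in the exploratory analyses may include but not be limited to the order of the experiments") and does not name the timing of the call.

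**The concern.** A rating with a seven-day recall shows persistence only if those seven days fall after stimulation. If the call comes early, the participant partly rates days on which she was being stimulated, and the score mixes the on-stimulation effect with the later effect.

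The crossover does not cancel this. The call after the active wave recalls active days and the call after the sham wave recalls sham days, so any difference between conditions during stimulation passes into the contrast used for objective 3.1.4. Hypotheses 4.2.1 and 4.2.2 predict such a difference. Once an early call has been made, its recall period cannot be repaired.

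**Working it through.** **Inputs.** Stimulation on Days 1-5 and 36-40 (Section 7.1). Call targets Day 12 and Day 47 (Section 8). Windows from Section 7.6.2 and Section 8, footnote b. Seven-day recall for both scales (Section 7.6.2).

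**The plan's own figure.** Last stimulation day plus seven: 5 + 7 = 12 and 40 + 7 = 47. The calendar targets reproduce.

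**Windows.**
- Section 7.6.2: 12 - 3 = 9 to 12 + 3 = 15; 47 - 3 = 44 to 47 + 3 = 50.
- Section 8: 12 - 1 = 11 to 15; 47 - 1 = 46 to 50.

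The late limits agree. The early limits differ by two days.

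**Stimulation days inside the recall.** For a call on day c, the recall covers c-6 to c if the call day is counted, or c-7 to c-1 if it is not. Counting the days up to Day 5 (wave 2 gives the same counts):

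| Call day | In 7.6.2 window | In Section 8 window | Call day counted | Not counted |
|---|---|---|---|---|
| 9 / 44 | yes | no | 3 | 4 |
| 10 / 45 | yes | no | 2 | 3 |
| 11 / 46 | yes | yes | 1 | 2 |
| 12 / 47 | yes | yes | 0 | 1 |
| 13-15 / 48-50 | yes | yes | 0 | 0 |

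Example: a Day 11 call recalls Days 5-11 (one stimulation day) or Days 4-10 (two). A Day 9 call recalls Days 3-9 (three) or Days 2-8 (four). With the rating day not counted, the Day 5 in-person rating itself covers four stimulation days (Days 1-4), so a Day 9 call can hold as many.

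**What overlap does to the contrast (illustration only).** Assume that all seven recalled days weigh equally, that the active-sham difference is D on each stimulation day, and that a fraction p of it truly remains afterwards. With k recalled stimulation days the phone contrast is D(k + (7-k)p)/7, and the excess over the true pD is k(1-p)D/7.
- Day 11 call, k = 1 to 2: between 1/7 = 0.14 and 2/7 = 0.29 of (1-p)D.
- Day 9 call, k = 3 to 4: between 3/7 = 0.43 and 4/7 = 0.57 of (1-p)D.

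These hold for a single call on that day. The average over a trial depends on the actual call days, which the documents do not give. The excess is zero if D = 0 or p = 1, and its sign follows D.

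**The case against.** **Section 8 is the designated source for windows.** Section 7.1 says so, and under Section 8 only Day 11/46 overlaps on both ways of counting. This stands as to size: the 3-4 day overlap arises only if staff follow Section 7.6.2. It does not remove the point, because nothing says that Section 8 overrides the instrument section and Section 8 itself still permits overlap.

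**Effects may really last.** Section 5.2 reports that in multiple sclerosis "improvements in subjective fatigue ratings have been demonstrated to persist for up to three weeks following tDCS", and two weeks in one breast cancer participant. If so, p is high and the excess small. That is fair, but persistence in this population is what objective 3.1.4 tests, so it cannot be assumed in advance.

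**The schedule should be kept closely.** Section 8 asks for this, so early calls may be few. Their number is unknown.

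**The seven days in Section 12.3 is a nominal label.** Agreed. Sections 3.1.4, 7.1 and 7.6.2 describe the call as approximately a week later. What is missing is only a stated way to handle call timing.

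A reader might infer three stronger things that the documents do not support:
- That the phone analysis carries a definite bias or a definite inflated false-positive rate. Any such figure needs call days, an effect shape, day weights and an effect size for these scales. None is given, and the 0.43 in Section 12.2 is for PASAT.
- That the bias must favour active stimulation. Section 9 lists moderate fatigue (35%) among effects during tDCS. It gives no sham rate, but if active stimulation adds short-lived fatigue, recalling those days would hide persistence on the MFSI-SF.
- That the main result is threatened. PASAT is not part of the phone call.

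**Conclusion.** The conflict is certain: the two windows differ by two days at the early limit in both waves. It is equally certain that each permits calls whose recall includes stimulation days: 1-2 of 7 at the earliest Section 8 call, 3-4 of 7 at the earliest Section 7.6.2 call, and none from Day 13/48.

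Whether this distorts the persistence result depends on there being an active-sham difference during stimulation that does not fully last. The direction can go either way. The size cannot be computed from the documents and is modest if Section 8 governs. Only the secondary persistence objective is affected; the PASAT endpoint, its paired t-test and the sample size of 45 completers are not. The point should be corrected because the text contradicts itself and the remedy is cheap.

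**What to change.** **Window.** Delete the plus-or-minus-three-day allowance in Sections 7.6.2.2 and 7.6.2.3. State one window there and in footnote b of Section 8 that opens no earlier than Day 12/47. For example, 0/+3 gives Days 12-15 and 47-50 and keeps the present late limit. Shift the wave 2 days by seven if the five-week washout is used (target 47 + 7 = Day 54, late limit 50 + 7 = Day 57).

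**Analysis.** Record the actual date of each call. In Section 12.3, add a sensitivity analysis that reports the active-sham contrast using only calls with no recalled stimulation days (Day 13/48 or later). State with it that it uses fewer data, measures a somewhat later time point and cannot separate recall overlap from true fading.

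A mixed model with the number of recalled days and its interaction with condition may look like a better use of the data, but it should not be adopted. Recalled days are a fixed function of time since stimulation. With weekday calls under 0/+3 the model only compares Friday calls (7 days after the fifth session) with Monday calls (10 days after). It would label real fading as recall overlap, and its contrast at zero overlap is a 10-day effect rather than the approximately 7-day effect in objective 3.1.4.

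**Cost.** Wording in three places, one recorded date per call and one extra analysis. Waves run Monday to Friday, so if calls are made on weekdays (an assumption), Section 8 now offers Thursday, Friday and Monday, while 0/+3 leaves Friday and Monday. One recalled stimulation day also remains at Day 12/47 if the call day is not counted, so the fix reduces the overlap but does not wholly remove it.
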